#### 9. Signed ICF

10. Age  $\geq$ 18

### **4.3 Exclusion criteria**

1. Stage IV disease
2. Receipt of adjuvant chemotherapy
3. Diagnosis of other invasive cancer except for adequately treated cervix cancer or skin cancer, or more than 5 years since other diagnosis of invasive cancer without current evidence of disease
4. Previous exposure to capecitabine, fluorouracil or immunotherapy with anti-PD1, anti-PDL1, anti-CTLA4 or similar drugs.
5. Active autoimmune disease that has required systemic treatment in the past 2 years; replacement therapy is not considered a form of systemic therapy. Autoimmune diseases include but are not limited to myasthenia gravis, myositis, autoimmune hepatitis, systemic lupus erythematosus, rheumatoid arthritis, inflammatory bowel disease, vascular thrombosis associated with antiphospholipid syndrome, Wegener's granulomatosis, Sjogren's syndrome, Guillain-Barre syndrome, multiple sclerosis, vasculitis or glomerulonephritis.
6. TB, active hepatitis B (defined as having a positive hepatitis B surface antigen [HBsAg]), active hepatitis C (defined as positive test for hepatitis C viral load by polymerase chain reaction [PCR]) or other active infection. Patients with past hepatitis B virus (HBV) infection or resolved HBV infection (defined as having a negative HBsAg test and a positive antibody to hepatitis B core antigen [anti-HBc] antibody test) are eligible. Patients with positive hepatitis C antibody and negative quantitative hepatitis C by PCR are eligible. Patients who have completed curative therapy for HCV are eligible. Patients with known HIV infection are eligible if they meet each of the following 3 criteria: CD4 counts  $\geq$  350 mm^3; serum HIV viral load of < 25,000 IU/ml and treated on a stable antiretroviral regimen.
7. History of (non-infectious) pneumonitis that required steroids or evidence of active pneumonia
8. Uncontrolled disease
9. Chronic use of systemic steroids
10. Live vaccine within 30 days prior to registration.
11. Incapacity to provide consent or to follow clinical trial procedures
12. Pregnancy, lactation, or planning to be pregnant

Patients with microsatellite unstable tumors will not be excluded as immunotherapy as adjuvant therapy is not standard for these patients but we will prospective collect this data.

## **4.4 Additional Study Restrictions**

### **4.4.1 Other Anticancer Therapy**

For purposes of this protocol, anti-tumor treatment may be defined as, but is not limited to, anti-cancer agents (endocrine therapy, cytotoxic chemotherapy, immunotherapy, or biologic therapy), radiotherapy, and investigational agents. An investigational agent is any drug or therapy not currently approved for use in humans. No other anticancer therapy is permitted during the course of the study treatment for any patient (the patient can receive a stable dose of corticosteroids during the study as long as these were started at least 4 weeks prior to enrollment and the total daily dose does not exceed 10mg of prednisone, or the equivalent, per exclusion criteria above). If the patient discontinues study treatment, this restriction no longer applies, however the patient will remain enrolled in the study for the purpose of collecting subsequent outcomes. Radiotherapy is not allowed.

### **4.4.2 Vaccines**

Live vaccine administration is not permitted within 30 days prior to the first dose of study treatment and while participating in the study. Examples of live vaccines include, but are not limited to, the following: measles, mumps, rubella, chicken pox, yellow fever, rabies, bacilli Calmette-Guerin (BCG), and typhoid (oral) vaccine. Seasonal influenza vaccines for injection are generally killed virus vaccines and are allowed. Intranasal influenza vaccines (eg, Flu-Mist®) are live attenuated vaccines, however, and are not allowed.

### **4.4.3 Birth Control**

Birth control should be used from the signing of the patient consent form and for 6 months following the last dose of nivolumab and capecitabine. Acceptable methods of birth control include:

- At least one highly effective form of contraception, defined as a contraceptive method with a failure rate of less than 1% per year when used consistently and correctly.
- Permanent sterilization, defined as hysterectomy, bilateral salpingectomy, bilateral oophorectomy, or bilateral orchiectomy
- Postmenopausal, defined as a female patient or sexual partner >45 years of age who has not menstruated for at least 12 consecutive months
- Total sexual abstinence

In addition, men must not donate sperm during nivolumab and capecitabine therapy and for seven months after receiving the last dose of study therapy.

### **4.4.4 Breast Feeding**

Patients must not breastfeed from the first dose and for 1 month following the final dose of nivolumab and capecitabine.

#### 4.4.5 Blood Donation

Patients must not donate blood during the study or for 90 days after the last dose of study treatment.

#### 4.4.6 Immunosuppressive Medication

Immunosuppressive medications including, but not limited to systemic corticosteroids at doses exceeding 10 mg/day of prednisone or equivalent, methotrexate, azathioprine, and TNF- $\alpha$  blockers are not allowed. Use of immunosuppressive medications for the management of investigational product-related AEs or in subjects with contrast allergies is acceptable. In addition, use of inhaled, intranasal, ophthalmic and topical corticosteroids is permitted. A temporary period of steroids will be allowed for different indications, at the discretion of the principal investigator (e.g., chronic obstructive pulmonary disease, radiation, nausea, etc).

### **4.5 Other Prior and Concomitant Therapy**

Any medication or vaccine (including over-the-counter or prescription medicines, vitamins and/or herbal supplements) that the subject is receiving at Screening up to the Final Visit must be recorded in source documents and the case report forms (CRFs). The reason for use, date(s) of administration (including start and end dates), and dosage information (including dose and frequency) must be recorded. Any change in concomitant therapy during the study period must be similarly recorded. Questions regarding prior or concomitant therapy should be directed to one of the investigators.

#### 4.5.1 Prior Surgery

Patients must have fully recovered from all effects of surgery. Patients must have had at least two weeks after minor surgery and four weeks after major surgery before starting therapy. Minor procedures requiring conscious sedation such as endoscopies or mediport placement may only require a 24-hour waiting period, but this must be discussed with an investigator.

#### 4.5.2 Supportive Care

Subjects should receive best supportive care and treatment of symptoms during the study as appropriate, including transfusion of blood and blood products, oxygen therapy, nutritional support, intravenous fluids, and treatment with appropriate medications (antibiotics, antiemetics, antidiarrheals, and analgesics, etc.). Medications that are given for supportive care, such as appetite stimulation, may be given concurrently.

##### 4.5.2.1 Bisphosphonates and denosumab

Bisphosphonates and denosumab are permitted for the treatment of osteopenia or osteoporosis, or as adjuvant treatment to decrease risk of breast cancer recurrence.

#### 4.5.2.2 Hematopoietic growth factors

Hematopoietic growth factors may be used according to the American Society of Clinical Oncology (ASCO) guidelines, but not during the first cycle of the study. The patient must be referred to a hematologist for further evaluation (1) if frequent transfusions are required or (2) if the treatment-related hematologic toxicities have not recovered to CTCAE Grade 1 or less after 4 weeks.

#### 4.5.3 For patients randomized to capecitabine (arms B and C), the approved label of capecitabine should be followed when concomitantly using:

- a. Anticoagulants, monitor anticoagulant response (INR or prothrombin time) frequently to adjust the anticoagulant dose as needed.
- b. Phenytoin, monitor phenytoin levels in patients.
- c. CYP2C9 substrates, caution should be exercised.

### **4.6 Removal/Replacement of Subjects from Therapy or Assessment**

An evaluable patient must meet all inclusion/exclusion criteria, have adequate tissue from definitive breast surgery for initial assessment, and be evaluable for the primary study endpoints of quantification of immune activation and immunomodulation, as well as the safety and tolerability of nivolumab and/or capecitabine.

#### 4.6.1 Screen Failures

Patients will be identified and enrolled after completing definitive breast surgery. All patients must continue to meet the inclusion and exclusion criteria up to and including the first day of treatment. Reasons for patients who have enrolled, but become ineligible could include (but are not limited to):

- The patient is no longer eligible based on laboratory parameters
- The patient's performance status has declined
- The patient does not have adequate tissue for initial assessment

Patients who become ineligible prior to initiation of therapy per protocol will be considered screen failures. Screen failures must be replaced until 45 patients with advanced triple negative breast cancer are enrolled.

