### **4.2 Inclusion Criteria**

#### **1. Biopsy proven TNBC:**

- ER- and PR- defined as  $\leq 5\%$  cells stain positive
- HER2 negativity defined as:
  - IHC 0, 1+ without in situ hybridization (ISH) HER2/neu chromosome 17 ratio OR
  - IHC 2+ and ISH HER2/neu chromosome 17 ratio non-amplified with ratio less than 2.0 and if reported average HER2 copy number  $< 6$  signals/cells

2. Residual disease of 1.0 cm at least of the primary tumor and/or node positive disease (at least ypN1) and/or Residual Cancer Burden (RBC) classification II or III. Tissue availability needs to be confirmed and should be received by the lead institution by day 1 of study treatment. (Note: As long as tissue sample is confirmed shipped, the subject will be eligible)

3. Patients must have completed neoadjuvant chemotherapy; patients must NOT have received capecitabine as part of their neoadjuvant therapy regimen. Acceptable preoperative regimens include an anthracycline or a taxane, or both. Participants who received preoperative therapy as part of a clinical trial may enroll. Participants may not have received adjuvant chemotherapy after surgery prior to randomization. Carboplatin-containing neoadjuvant chemotherapy is also allowed). Patients who cannot complete all planned neoadjuvant treatment cycles for any reason are considered high risk and therefore are eligible for the study if they have residual disease.

4. Recovery of all toxicities from previous therapies to at least grade 1, except alopecia and  $\leq$  grade 2 neuropathy which are allowed.

5. Must have completed definitive resection of primary tumor and have no evidence of unresected or metastatic disease at the time of study entry. For those who don't require radiotherapy, the most recent surgery for breast cancer must have been completed at least 14 days prior to day 1 of study treatment, but no more than 84 days prior to study registration.

- Negative margins for both invasive and ductal carcinoma in situ (DCIS) are desirable,

however patients with positive margins may enroll if the treatment team believes no further surgery is possible and patient has received radiotherapy; patients with margins positive for lobular carcinoma in situ (LCIS) are eligible

- Either mastectomy or breast conserving surgery (including lumpectomy or partial mastectomy) is acceptable

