#### 6. ECOG PS 0-1

7. Patients must not be planning to receive concomitantly other biologic therapy, hormonal therapy, other chemotherapy, surgery, radiation therapy or other anti-cancer therapy while receiving treatment on this protocol.

8. At the time of registration (randomization), patients must have the following laboratory results (obtained within 28 days prior to registration):

- a. A serum TSH prior to registration to obtain a baseline value.
- b. Patients must have adequate bone marrow function as evidenced by all of the following:
  - ANC  $\geq 1,500$  microliter (mcL);
  - Platelets  $\geq 100,000$ /mcL;
  - Hemoglobin  $\geq 9$  g/dL.
- c. Patients must have adequate hepatic function as evidenced by the following:
  - Total bilirubin  $\leq 1.5$  x institutional upper limit of normal (IULN) (except Gilbert's Syndrome, who must have a total bilirubin  $< 3.0$  mg/dL), and
  - SGOT (AST) or SGPT (ALT) and alkaline phosphatase  $\leq 2.5$  x IULN.
- d. Patients must have adequate renal function as evidenced by ONE of the following:
  - Serum creatinine  $\leq$  IULN OR
  - Measured or calculated creatinine clearance  $\geq 60$  mL/min.
- e. Normal thyroid function or stable on hormone supplementation (Patients that meet the definition of asymptomatic subclinical hypothyroidism will be eligible to participate)
- f. Women of childbearing potential (WOCBP) must have a negative urine or serum pregnancy test within 28 days prior to registration and within 24h prior to the start of nivolumab. In addition, women of childbearing potential must agree to have a pregnancy test every 4 weeks while on nivolumab.

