### **4.7.2 Patient Enrollment**

If a patient is being screened for enrollment, the local research coordinator must send an email within 24 hours containing the patient’s initials to the local PI, to [name], and to the Project Managers. If a patient is successfully screened, the local research coordinator must send all supporting documentation to the Project Managers(by secure email). Patients should not start therapy until [name] and the Project Managers have reviewed the patient’s records and confirmed that the patient is indeed eligible for enrollment.

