### **5.0 TREATMENT PLAN**

If a subject randomizes to Arm A, nivolumab will be provided by the study.

If a subject randomizes to Arm B, medication is not covered by the study and will be handled similarly to standard of care medication administration. Therapy will be based on the patient's actual weight. Dose adjustments will be made according to the approved label and at the discretion of the treating physician.

If a subject randomizes to Arm C, nivolumab will be provided by the study and capecitabine will be covered by patient's insurance.

Administration of nivolumab and/or capecitabine must be initiated within 2 weeks from enrollment in the study arm.

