#### **6.5. On Study Day 1**

Cycle 1 Day 1 testing need not to be repeated if completed within 14 days of starting therapy. Will be obtained blood samples for correlative studies (see Correlative Laboratory Manual for more details). Cycle 1 Day 1 must occur within 2 weeks after receiving randomization results.

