## **8.2 Sample Size Considerations**

The primary objective of the study is to assess the change in PIS, the Peripheral ImmunoScore, at 6 weeks (=2 cycles) from baseline, in each arm.

The sample size of 15 per arm (45 totally for 3 arms) is mainly based on the feasibility of patient accrual. A sample size of 15 per arm will have about 85% power to detect an effect size of 1 (the difference of the change in PIS from baseline to week 6 between two arms divided by the standard deviation) at 5% significance level.

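### Section 4.6.1 lets patients already randomised be relabelled screen failures and replaced up to day 1, with no all-randomised set for DRFS and OS

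*Combined protocol and SAP*

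**What the plan says.** - **Allocation.** Section 3.0 describes an open-label, three-arm randomised trial, and Section 6.4 randomises eligible patients. Section 4.2, criterion 8, treats registration and randomisation as one step: "At the time of registration (randomization), patients must have the following laboratory results".
- **Gap before treatment.** Section 6.5: "Cycle 1 Day 1 must occur within 2 weeks after receiving randomization results". Section 5.0 gives the same two weeks, counted from enrolment in the study arm.
- **Recheck and relabelling.** Section 4.6.1 requires all criteria to hold through day 1. It gives laboratory values, performance status and inadequate tissue as example reasons why an enrolled patient may become ineligible. It then says: "Patients who become ineligible prior to initiation of therapy per protocol will be considered screen failures". Screen failures are replaced until 45 patients are enrolled.
- **Central confirmation.** Under Section 4.7.2 therapy should not start until the lead investigator and the Project Managers have reviewed the records and "confirmed that the patient is indeed eligible for enrollment".
- **Tissue.** Section 6.2 wants availability and sufficiency confirmed before screening. The note to criterion 2 says: "As long as tissue sample is confirmed shipped, the subject will be eligible". Section 4.6 makes it a condition of being evaluable to "have adequate tissue from definitive breast surgery for initial assessment".
- **Analysis.** Section 8.5.2 plans Kaplan-Meier estimates and log-rank tests for DRFS and OS over 3 years of follow-up. Neither 8.4.2 nor 8.5.2 names the set of patients to be analysed.

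**The concern.** Once a patient has been randomised and the arm is known, any removal can depend on that arm, even without intent. Whether a borderline laboratory value is repeated, or a performance status re-graded, is a judgement made by people who know which treatment would follow. Calling the removed patient a screen failure places a post-randomisation loss in a category that normally holds patients who never entered the comparison.

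The stake is highest for the DRFS and OS log-rank tests, whose validity rests on the groups as randomised. Section 4.4.1 keeps patients who discontinue study treatment in the study for outcome collection. No section does the same for a patient who was randomised and never started.

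**Working it through.** **1. Order of events**

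| Step | Source | Arm known? |
|---|---|---|
| Consent, pre-registration, tissue sufficiency confirmed | 6.2 | No |
| Screening | 6.3 | No |
| Eligible patients randomised (= registered) | 6.4; 4.2 criterion 8 | From here, yes |
| Up to 2 weeks to Cycle 1 Day 1 | 6.5; 5.0 | Yes |
| All criteria must still hold; failure = screen failure, replaced | 4.6.1 | Yes, if already randomised |
| Latest time for central confirmation | 4.7.2 | Possibly |
| Baseline PIS blood drawn | 6.1 footnote; 6.5 | Yes |

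The 4.6.1 rule ends at day 1, so on its face it covers the interval after randomisation. One recheck in that interval is arm-specific: the pregnancy test within 24 hours of starting nivolumab (criterion 8f; 6.3) concerns arms A and C only.

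**2. The plan's own figure, and why power is not the issue**

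Inputs from 8.2 and 8.5.1: 15 per arm, effect size 1, 5% level, two-sample t-test, about 85% power. On the size, 8.2 says: "The sample size of 15 per arm (45 totally for 3 arms) is mainly based on the feasibility of patient accrual".

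- Noncentrality = 1/√(1/15 + 1/15) = 2.74, with 28 degrees of freedom.
- Power is 84.8% one-sided and 75.3% two-sided. The stated figure reproduces as a one-sided test of one arm against another. The documents do not state sidedness, which is a separate matter.
- With replacement the analysed number stays at 15, so these figures do not change. Without replacement, 14, 13 or 12 per arm would give one-sided power of 82.4%, 79.7% or 76.7%.

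**3. How many patients could be affected (assumed loss rates; none is given)**

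Number to randomise per arm = 15/(1 − loss), rounded up:

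- 5%: 15/0.95 → 16 per arm, 48 in total, 3 dropped.
- 10%: 15/0.90 → 17 per arm, 51 in total, 6 dropped.
- 20%: 15/0.80 → 19 per arm, 57 in total, 12 dropped.

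**4. DRFS and OS**

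Ignoring censoring, if k of n randomised patients in an arm are dropped, then (retained estimate) − (all-randomised estimate) = (k/n) × (retained − dropped). This cannot exceed k/n: 1/16 = 6.3, 2/17 = 11.8 or 3/18 = 16.7 percentage points. The limit needs every dropped patient to have the opposite outcome to every retained one, so real values would be well below it.

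For scale, take event-free proportions from Section 1.1, of 40% (recurrence-free at 2 years without pCR) and 69.8% (DFS on capecitabine in TNBC). These are related endpoints, not DRFS itself. The 95% half-width with 15 patients is:

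- 1.96 × √(0.40 × 0.60/15) = 24.8 points
- 1.96 × √(0.698 × 0.302/15) = 23.2 points

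**5. PIS**

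Suppose there is no true effect, one arm loses its worst 1 of 16, 2 of 17 or 3 of 18 patients, and the other loses none. With q the fraction lost and ρ the correlation between the selection factor and PIS change, the spurious shift is ρ × φ(z_q)/(1 − q).

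- q = 1/16, ρ = 0.3: 0.04 SD.
- q = 2/17, ρ = 0.5: 0.11 SD.
- q = 3/18, ρ = 0.5: 0.15 SD.

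Over ρ of 0.3 to 0.5, simulated type I error is about 5.2% to 6.9% two-sided and 6.2% to 10.7% one-sided, against a nominal 5%. All the loss falls in one arm here, which is an unfavourable assumption.

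**The case against.** The strongest reply is that 4.6.1 may mainly describe failures before randomisation. The documents do not define enrolled, and 4.6.1 speaks of patients enrolled after surgery, which is also when consent and pre-registration take place. That ambiguity stands. It does not remove the problem, because the rule runs to day 1, day 1 follows randomisation, and nothing limits the label to patients without an allocation.

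Several stronger readings are tempting and should not be drawn:

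- *Central confirmation happens after randomisation.* No section says so. Section 4.7.1 has the Project Managers confirm patients being considered for enrolment, 6.4 randomises eligible patients, and Appendix B is completed before registration. These point to an earlier check. What is missing is an explicit requirement: the only stated deadline in 4.7.2 is the start of therapy.
- *The shipped-tissue note waives sufficiency.* It relaxes receipt at the lead institution, and 6.2 still asks for sufficient material before screening. A tissue failure after allocation is left possible, not prescribed.
- *Lack of capecitabine coverage produces screen failures.* For arm B, Section 5.0 says "medication is not covered by the study", and in arm C capecitabine falls to the patient's insurance. Coverage is not an eligibility criterion, so 4.6.1 does not reach it.
- *The recheck is applied unevenly between sites.* Section 6.5 gives one rule for all sites, including the allowance for test results up to 14 days old.
- *These patients are stated to leave DRFS and OS follow-up.* This is an inference from the label and the missing analysis set.
- *Counting untreated patients would repair the PIS comparison.* Baseline PIS is drawn at Cycle 1 Day 1, so a patient removed earlier normally has no PIS change to contribute.

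**Conclusion.** The point holds in a limited form. The plan states a rule that, read as written, allows a randomised patient with a known arm to be relabelled and replaced before the first dose. It defines no all-randomised set that would keep that patient in the DRFS and OS comparisons. This is more than missing detail, because the stated rule itself permits the removal.

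The size is uncertain and probably modest. The window is at most two weeks, no pre-dose loss rate is given, and the ceilings for one to three losses in an arm (6.3 to 16.7 points) lie inside the sampling error of a 15-patient arm. Replacement protects nominal power, so the cost is possible selection and an incomplete account of who was randomised. The conclusion assumes that some of the patients 4.6.1 describes have already been randomised.

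The replacement of patients taken off study before two cycles (4.6.2.1, 8.5.1) is a separate post-randomisation exclusion and probably a larger one. Correcting that rule would leave 4.6.1 as it is.

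**What to change.** 1. **4.6.1:** restrict screen failure to patients who fail before randomisation.
2. **4.7.2:** require central eligibility confirmation, including the tissue sufficiency already asked for in 6.2, before the allocation is released.
3. **8.5.2:** analyse DRFS and OS in all randomised patients as assigned. Report every randomised patient by arm, with the reason where treatment was not started, and follow untreated patients for both endpoints.
4. **4.6 and 8.5.1:** keep the PIS analysis in patients with baseline and week-6 samples, and remove tissue adequacy as a condition for it, since 9.1 measures PIS on blood cells. Extra patients may still be enrolled to reach 15 per arm with PIS samples.

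Items 1 and 2 act by preventing avoidable losses after allocation. Item 3 protects DRFS and OS and does not change the PIS data. The cost is a wording amendment, a short delay before randomisation, and a few untreated patients in the DRFS and OS denominators. If accrual has closed, items 3 and 4 can still be applied, apart from the extra enrolment.
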